4.2. Inclusion Criteria (Parts A and B)

Patients must meet all of the following inclusion criteria to be eligible to enroll in this study:

1. Written informed consent obtained prior to any screening procedures and in accordance with federal, local, and institutional guidelines.
2. Age ≥ 18 years.
3. Patients with advanced solid malignancies or NHL for which all standard therapeutic options considered useful by the investigator have been exhausted.
4. Patients must have objective evidence of progressive disease on study entry:
 - a. Advanced solid malignancies: Measurable disease as defined by RECIST 1.1 ([Appendix 4](#)).
 - b. NHL: Measurable disease including target lesion(s) as defined by the Lugano Classification for initial evaluation and staging ([Appendix 3](#)).
5. Patients must have a site of disease amenable to biopsy and be a candidate for biopsy according to the treating institution's guidelines.
6. Eastern Cooperative Oncology Group (ECOG) performance status of ≤ 1 .
7. Adequate hepatic function:
 - a. Total bilirubin < 1.5 times the upper limit of normal (ULN) (except patients with Gilbert's syndrome [hereditary indirect hyperbilirubinemia] who must have a total bilirubin of ≤ 3 times ULN),
 - b. Aspartate aminotransferase (AST) and alanine aminotransferase (ALT) ≤ 2.5 times ULN (except patients with known liver involvement of their advanced solid malignancy or NHL who must have their AST and ALT ≤ 5.0 times ULN).
8. Adequate renal function: estimated creatinine clearance of ≥ 60 mL/min, calculated using the formula of Cockroft and Gault $(140 - \text{Age}) \cdot \text{Mass (kg)} / (72 \cdot \text{creatinine mg/dL})$; multiply by 0.85 if female.
9. Female patients of child-bearing potential must agree to use dual methods of contraception (including one highly effective and one effective method of contraception [as defined in Section [6.9.2.2](#)]) and have a negative serum pregnancy test at Screening, and male patients must use an effective barrier method of contraception if sexually active with a female of child-bearing potential. For both male and female patients, effective methods of contraception must be used throughout the study and for 3 months following the last dose.

10. Adequate hematopoietic function: total white blood cell (WBC) count $\geq 1500/\text{mm}^3$, absolute neutrophil count (ANC) $\geq 1000/\text{mm}^3$, hemoglobin (Hb) $\geq 10.0 \text{ g/dL}$, and platelet count $\geq 75,000/\text{mm}^3$.
11. Dose Escalation Phase: Patients will be enrolled according to their NAPRT1 status at a ratio of 2:1 (NAPRT1 negative:NAPRT1 positive). The NAPRT1 status must be determined prior to enrollment based on evaluation of a fresh tumor biopsy or archival tissue taken ≤ 6 months of screening.
12. Dose Expansion Phase (KPT-9274 \pm niacin ER cohort only): Patient tumors NAPRT1 and IDH1 status must be determined at the central laboratory prior to enrollment.
 - a. Confirmation of NAPRT1 expression and IDH1 mutation based on evaluation of a fresh tumor biopsy or archival tumor biopsy taken ≤ 6 months of screening tests as follows:
 - i. NAPRT1 positive for expansion cohort I or III
 - ii NAPRT1 negative for expansion cohort II or III
 - iii. IDH1 mutation status for expansion cohort IV
13. Life expectancy of ≥ 3 months.

4.3. Exclusion Criteria (Parts A and B)

Patients meeting any of the following exclusion criteria are not eligible to enroll in this study:

1. Female patients who are pregnant or lactating.
2. Time since the last prior therapy for treatment of advanced solid malignancies or NHL**:
 - a. Radiation, chemotherapy, immunotherapy or any other anticancer therapy, including investigational anti-cancer therapy ≤ 2 weeks prior to C1D1.
 - b. Palliative steroids for disease related symptoms < 7 days prior to C1D1.

**Patients must have recovered or stabilized (Grade 1 or to their baseline for non-hematologic toxicities, \leq Grade 2 or to their baseline for hematologic toxicities) from toxicities related to their previous treatment except for alopecia. In specific cases, patients with Grade 2 non-hematologic toxicities will be allowed following approval by the Karyopharm medical monitor.

3. Patients with known central nervous system (CNS) disease or leptomeningeal involvement, regardless of response to prior therapy, are excluded.
4. Major surgery within four weeks before C1D1.
5. Impaired cardiac function or clinically significant cardiac diseases, including any of the following:
 - a. Unstable angina or acute myocardial infarction ≤ 3 months prior to C1D1;
 - b. Clinically significant heart disease (e.g., symptomatic congestive heart failure; uncontrolled arrhythmia, or hypertension; history of labile hypertension or poor compliance with an antihypertensive regimen).

6. Active infection with completion of therapeutic antibiotics, antivirals, or antifungals within one week prior to C1D1. Prophylactic antibiotics, antivirals or antifungals are permitted.
7. Patients with a known history of Human Immunodeficiency Virus (HIV); HIV testing is not required as part of this study.
8. Known, active hepatitis A, B, or C infection; or known to be positive for HCV RNA or HBsAg (HBV surface antigen). Testing is not required.
9. Patients with significantly diseased or obstructed gastrointestinal tract or uncontrolled vomiting or diarrhea that could interfere with the absorption of KPT-9274.
10. Serious psychiatric or medical conditions that, in the opinion of the Investigator, could interfere with treatment, compliance, or the ability to give consent.
11. Active peptic ulcer disease or other active gastrointestinal bleeds.

4.4. Inclusion Criteria (Part C)

Patients must meet all of the following inclusion criteria to be eligible to enroll in this study.

1. Written informed consent obtained prior to any screening procedures and in accordance with federal, local, and institutional guidelines.
2. Age ≥ 18 years.
3. Patients must have objective and measurable melanoma by RECIST 1.1 after disease progression on a prior anti-PD-1 or anti-PD-L1 therapy.
4. Eastern Cooperative Oncology Group (ECOG) performance status of ≤ 2
5. Adequate hepatic function:
 - a. Total bilirubin < 1.5 times the upper limit of normal (ULN) (except patients with Gilbert's syndrome [hereditary indirect hyperbilirubinemia] who must have a total bilirubin of ≤ 3 times ULN),
 - b. Aspartate aminotransferase (AST) and alanine aminotransferase (ALT) ≤ 2.5 times ULN (except patients with known liver involvement of their advanced solid malignancy who must have their AST and ALT ≤ 5.0 times ULN).
6. Adequate renal function: Estimated creatinine clearance of ≥ 60 mL/min, calculated using the formula of Cockroft and Gault $(140 - \text{Age}) \cdot \text{Mass (kg)} / (72 \cdot \text{creatinine mg/dL})$; multiply by 0.85 if female.
7. Female patients of child-bearing potential must agree to use dual methods of contraception (including one highly effective and one effective method of contraception) and have a negative serum pregnancy test at Screening, and male patients must use an effective barrier method of contraception if sexually active with a female of child-bearing potential. For both male and female patients, effective methods of contraception must be used throughout the study and for 3 months following the last dose.

8. Adequate hematopoietic function: total white blood cell (WBC) count $\geq 1500/\text{mm}^3$, absolute neutrophil count (ANC) $\geq 1000/\text{mm}^3$, hemoglobin (Hb) $\geq 10.0 \text{ g/dL}$, and platelet count $\geq 100,000/\text{mm}^3$.
9. Life expectancy of ≥ 3 months.

4.5. Exclusion Criteria (Part C)

Patients meeting any of the following exclusion criteria are not eligible to enroll in this study:

1. Female patients who are pregnant or lactating.
2. ≤ 2 weeks since the last prior therapeutic regimen for melanoma. Palliative steroids for disease related symptoms < 7 days prior to C1D1, unless physiologic doses of steroids are used.
3. Patients who have not recovered or stabilized (Grade 1 or to their baseline for non-hematologic toxicities, \leq Grade 2 or to their baseline for hematologic toxicities) from toxicities related to their previous treatment except for alopecia. In specific cases, patients with Grade 2 non-hematologic toxicities will be allowed following approval by the Karyopharm medical monitor.
4. Patients with untreated central nervous system (CNS) disease or leptomeningeal involvement are excluded. Patients without active brain or leptomeningeal metastases after prior treatment with local therapies are eligible provided that the treatment had been done ≥ 2 weeks prior to enrollment.
5. Major surgery within four weeks before C1D1.
6. Active infection with completion of therapeutic antibiotics, antivirals, or antifungals within one week prior to C1D1. Prophylactic antibiotics, antivirals or antifungals are permitted.
7. Patients with significantly diseased or obstructed gastrointestinal tract or uncontrolled vomiting or diarrhea that could interfere with the absorption of KPT-9274.
8. Serious psychiatric or medical conditions that, in the opinion of the Investigator, could interfere with treatment, compliance, or the ability to give consent.
9. Active peptic ulcer disease or other active gastrointestinal bleeds.
10. Patients requiring treatment with corticosteroids at doses higher than substitute therapy ($> 10 \text{ mg prednisone}$), are unstable with substitute hormonal therapy, or are deemed to be likely to re-occur by the treating physician when administered nivolumab.

4.6. Screening and Registration

The Screening period starts once a patient has provided written informed consent to participate in the study and ends on the day of study entry (C1D1).

Patient eligibility (inclusion/exclusion criteria) will be reviewed for each patient participating in the study by the Karyopharm Medical Monitor before the patient receives study treatment on C1D1. The procedure used to check eligibility and registration of patients is the same in the Dose Escalation Phase and the Dose Expansion Phase of the study, as follows:

The eligibility check form/Patient Registration Form will be sent from the site to Karyopharm for evaluation either by fax or email. Upon confirmation of eligibility, Karyopharm will return the signed eligibility check form/Patient Registration Form via fax or email to the site. The Patient Registration Form will indicate the dose group to which the patient has been assigned (see Section 4.6.1).

4.6.1. Study Patient Number

Upon screening, each patient will be assigned a unique patient number and will keep this number for the duration of the study. Patient numbers will not be reassigned or reused for any reason. Patients will be identified to Karyopharm by their assigned number, initials, date of birth, and sex. The Investigator must maintain a patient master log.

4.6.2. Rescreening

Rescreening is permitted in this study following discussion with the Karyopharm Medical Monitor. If a patient fails any of the inclusion or exclusion criteria, that patient may be rescreened after a suitable period of time (the exact length is dependent upon the reason for the screen failure) at the agreement of the Karyopharm Medical Monitor and the Investigator. Any patient who is rescreened must be re-consented. A patient may only be re-screened once.

4.6.3. Screen Failures

Patients who sign an informed consent but fail to start on treatment for any reason will be considered a screen failure. Date of consent and reason for ineligibility will be entered into the clinical database. No other data will be entered into the clinical database for patients who are screen failures, unless those patients experience serious adverse event (SAE) during the Screening Phase.

5. DISCONTINUATION CRITERIA

5.1. Early Termination of the Study

This study may be discontinued at the sole discretion of Karyopharm for any reason, including medical or ethical reasons affecting the continued performance of the study, or difficulties in the recruitment of patients. If this occurs, Karyopharm will notify ethics committees, Investigators, and regulatory authorities, as applicable.

5.2. Discontinuation of Study Treatment and/or Withdrawal of Patients from the Study

The Investigator may remove a patient from study treatment after consultation with the Karyopharm Medical Monitor for any of the following reasons:

- Unacceptable AEs or toxicity that cannot be managed by supportive care
- Any medically appropriate reason (e.g., clinical progression) or significant protocol violation, in the opinion of the Investigator

The Investigator must remove a patient from study treatment for any of the following reasons:

- Disease progression per response criteria
- Patient withdraws consent to continue study treatment
- Pregnancy

Patients who are removed from study treatment by the Investigator are not permitted to restart study treatment.

Patients may discontinue study treatment for any reason. Patients who choose to discontinue study treatment should be encouraged to continue in the study so that follow-up information on disease progression and survival status may be obtained. Patients may elect to withdraw consent and decline further participation in the study at any time. If a patient withdraws consent after completing Cycle 1, he/she may request to re-enter the study, if it occurs within 28 days since the last dose, by re-signing consent. This is permitted based on the Investigator's discretion and after consultation with the Karyopharm Medical Monitor.

The reason for the patient's discontinuation of study treatment/withdrawal from the study must be recorded on the eCRF.

All patients will be followed until PD, withdrawal of consent, occurrence of any withdrawal criteria, intolerable toxicity precluding further treatment with study treatment, death or loss to follow up.

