18 Telephone call (or visit) with patient to evaluate supportive care medications, concomitant medications, adverse events, and serious adverse events, and to adjust supportive care as appropriate. The telephone contact with the patient must take place Cycle 1 Days 4 +1day, 11 and 18 \pm 1 day; Cycle 2 and beyond – Days 4, 11, 18, and 25 \pm 1 day; Safety Follow-up phone call +7 days; and durability of response \pm 7 days if the in person visit is not performed.

19 If feasible and clinically indicated, the following assessments should be performed every 3 months for 1 year after the Safety Follow-up Visit/Call for patients who have not progressed to assess durability of response: PET/CT for FDG-avid lymphomas, or CT for non-FDG-avid lymphomas (or PET/MRI or MRI, respectively, if CT is contraindicated) scans for NHL patients and CT, MRI, or PET-CT scans for solid malignancy patients. If these assessments cannot be performed, and for patients with PD, a telephone call will be made to the patient (or the patient's family) every 3 months for 1 year to inquire about the patient's survival, disease status, and overall medical condition, and information on any antineoplastic therapies utilized since discontinuation of KPT-9274 study treatment.

20 See Table 4 for at home versus in-clinic visit dosing.

21 These assessments are to be completed pre-dose on C1D1 and are to be used to establish baseline values, not to reconfirm eligibility. However, if a safety concern is noted, contact Karyopharm.

22 Safety follow-up telephone call [30 days post-last dose (+ 7 days)] with patient after their last dose of study treatment to evaluate their overall medical condition and status of disease, AEs, including follow-up on any AEs that were not resolved at the EoT Visit, and collection of information on any antineoplastic therapies used after discontinuation of study treatment.

23 At the Investigator's discretion, in consultation with the Karyopharm Medical Monitor, patients with clinically significant joint or muscle-related AEs may have a rheumatology consultation. Rheumatology testing may be completed as clinically indicated per institutional standards (e.g., antinuclear antibodies, rheumatoid factor, C-reactive protein, erythrocyte sedimentation rate, uric acid [if not already available], or other autoantibodies based on symptoms).

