6.2.8. KPT-9274 Dose Reduction Guidelines for Toxicity

For Grade 2 toxicities present at baseline, the drug will not be held and the treating investigator will closely monitor and support the patient.

Patients are expected to be aggressively treated to minimize the likelihood and/or severity of side effects at the discretion of the Investigator (consultation with the Karyopharm Medical Monitor is strongly encouraged), particularly GI symptoms and hematopoietic toxicities as observed in KPT-9274 animal toxicology studies. See Section [6.9.1](#) for supportive care details.

For patients who do not tolerate the protocol-specified dosing schedule, KPT-9247 dose adjustments are permitted in order to allow the patient to continue the study treatment. The criteria for dose modifications of KPT-9274 for toxicities are outlined in [Table 15](#). These changes must be recorded on the eCRF. If a patient requires a dose delay of more than 28 days (> 28 days) from the intended day of the next scheduled dose, then the patient should be discontinued from the study (in exceptional situations, if the patient is clearly benefiting from the study treatment, and in the opinion of the Investigator no safety concerns are present, after discussion with the Karyopharm Medical Monitor, the patient may remain in the study).

If, after interruption of treatment and resolution of the event, treatment is resumed at the same dose and the same toxicity reoccurs with the same severity, the next treatment re-initiation must resume at the next lower dose level, irrespective of duration. Patients who do not recover (i.e., ≤ Grade 1 or baseline) within 28 days (≤ 28 days) of discontinuation of study treatment will not be permitted to re-start study treatment and will be discontinued from the study.

In the event of a DLT (Cycle 1) during the Dose Escalation Phase the patient must discontinue KPT-9274.

In the event of any other toxicity (< Grade 3) during the Dose Escalation Phase, one of the following actions may be taken at the Investigator's discretion after consulting with the Karyopharm Medical Monitor:

- Patients can continue treatment with KPT-9274 without a dose delay or reduction.
- If the decision is made to hold KPT-9274:

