\geq Grade 3	
Optimal supportive care medications according to institutional guidelines or NCCN Clinical Practice Guidelines in Oncology should already be instituted. Also refer to Benson Guidelines.
 
Hold KPT-9274 until the event resolves to \leq Grade 1 or baseline (as appropriate):
 
 First occurrence of \geq Grade 3: 
 If supportive care results in the AE improving to Grade \leq 1 or baseline within 3 days (\leq 3 days), restart KPT-9274 at the current dose. If the improvement to Grade \leq 1 or baseline takes longer than 3 days ($>$ 3 days), KPT-9274 should be resumed at one dose level lower (see Table 15). Second or greater occurrence of \geq Grade 3, restart KPT-9274 at one dose level lower (see Table 15) upon improvement to Grade \leq 1 or baseline irrespective of duration. 
**If the toxicity does not resolve to \leq Grade 1 or baseline within 28 day (\leq 28 days), study treatment will be discontinued permanently.
 
**If, after interruption of treatment and resolution, treatment is resumed at the same dose and the same toxicity reoccurs with the same severity, next treatment re-initiation must resume at the next lower dose level, irrespective of duration.

Toxicity and Intensity	Dose Modification
Hematological Toxicity	
Thrombocytopenia	
Grade 2	Maintain dose

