8.1.2. Recording of Adverse Events

Adverse Events will be reported and recorded in the eCRF from the time of the first dose of study drug through 30 days after the last dose of study drug or until the start of subsequent antineoplastic therapy, whichever occurs first. That is, if a patient begins a new antineoplastic therapy, the AE reporting period for nonserious AEs ends at the time the new treatment is started.

Adverse events (including laboratory abnormalities that constitute AEs) should be described using a diagnosis whenever possible, rather than individual underlying signs and symptoms. When a clear diagnosis cannot be identified, each sign or symptom should be recorded as a separate AE.

The Investigator should ask the patient non-leading questions to determine if any AEs have occurred during the study, since the last study visit. Adverse events may also be recorded when they are volunteered by the patient, or through physical examination, laboratory tests, or other clinical assessments.

An AE should be followed, and an assessment should be made at each visit (or more frequently, if necessary) for any changes in severity of the event, the suspected relationship to the study treatment, the interventions required to treat the event, and the outcome.

All AEs occurring during the study are to be followed up in accordance with good medical practice until they are resolved, stabilized or judged no longer clinically significant or, if a chronic condition, until fully characterized.

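### Protocol Sections 5.2 and 6.2.8, read literally, end follow-up at PD, intolerable toxicity or 28 days without recovery, contradicting the scheduled safety call, AE follow-up and 1-year survival calls

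*Protocol*

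**What the plan says.** Two places in the protocol end a patient's participation.

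- Section 5.2, last sentence: "All patients will be followed until PD, withdrawal of consent, occurrence of any withdrawal criteria, intolerable toxicity precluding further treatment with study treatment", followed by death and loss to follow-up.
- Section 6.2.8: patients not back to Grade 1 or baseline within 28 days of stopping treatment "will not be permitted to re-start study treatment and will be discontinued from the study". For a dose delay of more than 28 days, "then the patient should be discontinued from the study (in exceptional situations", with the exception covering patients who are clearly benefiting.

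Other current text treats the same situations differently.

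- Table 16, for toxicity unresolved at 28 days: "study treatment will be discontinued permanently". It says nothing about leaving the study.
- Section 5.2 itself: patients who choose to stop treatment "should be encouraged to continue in the study so that follow-up information on disease progression and survival status may be obtained".
- Section 3.1: a follow-up period (EoT visit, safety follow-up, durability and survival follow-up) belongs to every phase.
- Tables 3 and 7, with footnote 22 (Parts A and B) and footnote 16 (Part C): a safety call 30 days (+7) after the last dose, covering AEs still open at EoT.
- Section 7.5.3.1: AEs and SAEs are collected for 30 days after the last dose.
- Section 8.1.2: "All AEs occurring during the study are to be followed up in accordance with good medical practice until they are resolved", stabilized or otherwise settled. Section 8.2.2 asks the same for SAEs, until resolution or until judged permanent.
- Footnote 19 (Parts A and B) and footnote 13 (Part C): where follow-up scans cannot be done, "and for patients with PD, a telephone call will be made to the patient" or family every 3 months for 1 year. SAP Section 1.5 repeats the 3-monthly calls.

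**The concern.** A site has two incompatible instructions for the same patient. One says that follow-up of all patients stops at PD or at treatment-ending toxicity. The other schedules safety and survival contacts after exactly those events. This is a stated rule that conflicts with the schedule, not a missing detail.

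Two things are at stake. OS is an endpoint in every part, and a survival endpoint needs contact after progression. In addition, the patients covered by the 28-day rule are by definition those whose toxicity is still open. Their course is what Sections 8.1.2 and 8.2.2 require to be followed, and this is a first-in-human study.

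**Working it through.** The plan gives no figure on this point to reproduce. The check is a comparison of texts plus one comparison of time limits.

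**1. Patient with PD.** The last sentence of 5.2 ends follow-up at PD. Footnotes 19 and 13 require calls for 1 year for patients with PD. Both cannot be followed. Scans are not in conflict here, because the follow-up scans are only for patients who have not progressed. The conflict at PD concerns the safety and survival contacts.

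**2. Consequence for OS.** Protocol Section 9.5 censors OS at last contact for patients who withdraw from the study or are alive. SAP Table 4-1 censors at study discontinuation or at the last visit or contact with the patient alive. If contact ends at PD, a progressed patient is censored at about the date of PD. The only deaths counted are those before documented PD. That censoring is informative, since progression bears on survival.

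**3. Patient with unresolved toxicity.** Section 6.2.8 states two consequences for non-recovery: no restart, and removal from the study. Table 16 states one: permanent stop of study treatment. A DLT in Cycle 1 of escalation also has only a treatment consequence: "In the event of a DLT (Cycle 1) during the Dose Escalation Phase the patient must discontinue KPT-9274". The protocol therefore does not use one rule for leaving the study.

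**4. Timing.** Inputs: non-recovery limit 28 days (Section 6.2.8); safety call from day 30 to day 30 + 7 = 37 after the last dose; AE window to day 30.

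- If the 28 days run from the last dose, removal comes 30 − 28 = 2 to 37 − 28 = 9 days before the safety call, and 30 − 28 = 2 days before the AE window closes.
- If they run from the first dose not given, the clock starts later. On the regular schedule (Days 1, 3, 5, 8) doses are 2 or 3 days apart, so the limit falls at 28 + 2 = 30 or 28 + 3 = 31 days after the last dose. The call may then already have been made, or may be up to 37 − 30 = 7 days away.
- The delay rule counts from the next scheduled dose, so it takes effect beyond day 30 or 31, inside the call window.

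On any of these counts the 3-monthly contacts, which start after the safety call, are still to come. A non-recovered patient's AE is also still open under Section 8.1.2.

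**5. Section 5.2 against itself.** The encouragement to stay for progression and survival information is addressed to patients who choose to stop. Patients removed by the investigator for PD or toxicity are left with the closing sentence.

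**The case against.** The strongest reply is that the closing sentence of 5.2 is loose end-of-treatment wording. Its list closely tracks the treatment-duration list in Section 3.3, and the detailed schedule, the footnotes and the SAP all point the other way. In 6.2.8 the exception lets a benefiting patient remain in the study, which suggests that the word study is standing in for treatment. This is a plausible account of how the text arose. It does not settle what a site should do, because the sentence says that all patients are followed until these events and 6.2.8 lists removal from the study in addition to the bar on restarting. It does mean that a site working from Tables 3 and 7 would keep the data.

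Several stronger readings might be inferred, and the documents do not support them.

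- **That the primary safety endpoint is lost.** The endpoint is the occurrence of Grade 3 or higher AEs, SAEs and AEs leading to discontinuation. Events that lead to discontinuation are recorded before the patient leaves; what is at risk is their later course.
- **That patients stopped for toxicity have no further scans.** Footnotes 12 and 15, and footnote 20 in Part C, require an EoT scan for patients who stop for reasons other than progression. Later scans are only if feasible and clinically indicated, so sparse imaging after that comes from the schedule itself.
- **That the 28-day rule will apply often because anemia is common.** Table 11 gives 22 + 1 = 23 of 47 patients (48.9%) with Grade 3 or 4 treatment-related anemia. Table 16 only asks sites to consider holding for it and allows dosing to continue with support. More than 3 doses missed in the first 28 days for drug-related toxicity is itself a DLT, and Section 1.2.1 reports 2 DLTs in 47 patients. Long toxicity holds were therefore rare in Cycle 1; later cycles are not reported.
- **That 6.2.8 takes all toxicity patients off the study.** It covers only non-recovery within 28 days or a delay beyond 28 days, and the delay rule has an exception.

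**Conclusion.** The contradiction is real and stands in current text. Under a literal reading of 5.2, OS is censored at PD. Under a literal reading of 6.2.8, a patient with an unresolved AE can be closed out 2 to 9 days before the safety call, assuming that the 28 days run from the last dose. The number of patients affected cannot be stated: neither document gives how many stopped for PD or toxicity, or how sites have read these sections. Loss of data is a risk that depends on which text a site follows, not a certainty. It would go too far to say that OS cannot be measured in this trial, because the calls that would measure it are scheduled.

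**What to change.** In Section 5.2, replace the last sentence with one saying that patients who stop treatment for any reason, including PD and toxicity, complete the EoT visit, the 30-day safety call and the 3-monthly follow-up for 1 year, unless they die, withdraw consent to follow-up or are lost. Open AEs and SAEs continue to be followed under Sections 8.1.2 and 8.2.2.

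In Section 6.2.8, reconcile with Table 16 both statements that take a patient off the study, together with the exception that lets a patient remain in it, so that end of treatment and end of study are separate terms. No treatment-stopping rule needs to change for this, and which rule applies is for the sponsor to settle.

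The cost is protocol wording. The visits and calls are already in Tables 3 and 7, so no new assessment is added.
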